#### **4.2.2 Rationale for Dose Selection/Regimen/Modification**

An open-label Phase I trial (Protocol 001) is being conducted to evaluate the safety and clinical activity of single agent MK-3475. The dose escalation portion of PN001 evaluated three dose levels, 1 mg/kg, 3 mg/kg, and 10 mg/kg, administered every 2 weeks (Q2W) in subjects with advanced solid tumors. All three dose levels were well tolerated and no dose-limiting toxicities were observed. This first in human study of MK-3475 showed evidence of target engagement

9458- Protocol Version Date 28 Feb 2019

and objective evidence of tumor size reduction at all dose levels (1 mg/kg, 3 mg/kg and 10 mg/kg Q2W). No MTD has been identified to date. 10.0 mg/kg Q2W, the highest dose tested in PN001, will be the dose and schedule utilized in Cohorts A, B, C and D of PN001 to test for initial tumor activity. Recent data from other clinical studies within the MK-3475 program has shown that a lower dose of MK-3475 and a less frequent schedule may be sufficient for target engagement and clinical activity.

PK data analysis of MK-3475 administered Q2W and Q3W showed slow systemic clearance, limited volume of distribution, and a long half-life (refer to IB). Pharmacodynamic data (IL-2 release assay) suggested that peripheral target engagement is durable (>21 days). This early PK and pharmacodynamic data provides scientific rationale for testing a Q2W and Q3W dosing schedule.

A population pharmacokinetic analysis has been performed using serum concentration time data from 476 patients. Within the resulting population PK model, clearance and volume parameters of MK-3475 were found to be dependent on body weight. The relationship between clearance and body weight, with an allometric exponent of 0.59, is within the range observed for other antibodies and would support both body weight normalized dosing or a fixed dose across all body weights. MK-3475 has been found to have a wide therapeutic range based on the melanoma indication. The differences in exposure for a 200 mg fixed dose regimen relative to a 2 mg/kg Q3W body weight based regimen are anticipated to remain well within the established exposure margins of 0.5 – 5.0 for MK-3475 in the melanoma indication. The exposure margins are based on the notion of similar efficacy and safety in melanoma at 10 mg/kg Q3W vs. the proposed dose regimen of 2 mg/kg Q3W (i.e. 5-fold higher dose and exposure). The population PK evaluation revealed that there was no significant impact of tumor burden on exposure. In addition, exposure was similar between the NSCLC and melanoma indications. Therefore, there are no anticipated changes in exposure between different indication settings.

The rationale for further exploration of 2 mg/kg and comparable doses of pembrolizumab in solid tumors is based on: 1) similar efficacy and safety of pembrolizumab when dosed at either 2 mg/kg or 10 mg/kg Q3W in melanoma patients, 2) the flat exposure-response relationships of pembrolizumab for both efficacy and safety in the dose ranges of 2 mg/kg Q3W to 10 mg/kg Q3W, 3) the lack of effect of tumor burden or indication on distribution behavior of pembrolizumab (as assessed by the population PK model) and 4) the assumption that the dynamics of pembrolizumab target engagement will not vary meaningfully with tumor type.

The choice of the 200 mg Q3W as an appropriate dose for the switch to fixed dosing is based on simulations performed using the population PK model of pembrolizumab showing that the fixed dose of 200 mg every 3 weeks will provide exposures that 1) are optimally consistent with those obtained with the 2 mg/kg dose every 3 weeks, 2) will maintain individual patient exposures in the exposure range established in melanoma as associated with maximal efficacy response and 3) will maintain individual patients exposure in the exposure range established in melanoma that are well tolerated and safe.

A fixed dose regimen will simplify the dosing regimen to be more convenient for physicians and to reduce potential for dosing errors. A fixed dosing scheme will also reduce complexity in the logistical chain at treatment facilities and reduce wastage.

9458- Protocol Version Date 28 Feb 2019

### 4.2.3 Rationale for Endpoints

#### 4.2.3.1 Efficacy Endpoints

Immunotherapy is a particularly attractive approach to the problem of MRD persistence/reappearance: the disease burden by definition is very low; and when MRD is detected following multiple cytotoxic agents, additional cytotoxic therapy is unlikely to provide substantial efficacy but could lead to significant toxicity. Proof of this principle has been demonstrated with blinatumomab, a CD3-CD19 bispecific antibody that helps target the patient's endogenous CD3+ T cells to the CD19+ blasts in B-cell precursor ALL. Early in its development, this agent was shown to be efficacious against chemorefractory MRD in adults with ALL, with 16 of 20 patients remaining in hematologic remission at a median follow-up of 405 days (relapse-free survival of 78%). Similar results were observed in a larger study from the German Multicenter ALL Study Group. It is now being tested in a randomized Phase III study (ClinicalTrials.gov #NCT02013167), and it was granted accelerated approval by the Food and Drug Administration in December 2014. Unfortunately, blinatumomab must be administered as a 28-day continuous intravenous (IV) infusion, making it very inconvenient for the patient and the clinical staff. Furthermore, it is associated with significant toxicity, including serious neurologic side-effects and cytokine release syndrome. While it can be highly efficacious in this setting, blinatumomab is not universally effective. Further, due to its toxicity profile and need for 4-week continuous infusion (a portion of which must be administered in an inpatient setting), patients may not be eligible or willing to receive it. Immune checkpoint blockade through inhibition of the PD-1/PD-L1 axis could provide a similar benefit for a very high-risk clinical scenario with relatively low toxicity, a significantly easier mode of administration, and inclusion of both T- and B-cell ALL.

Thus, based on the ability of immunotherapy to eliminate MRD, the belief that this endpoint will translate into improved long-term outcomes in ALL, as well as a strong need for new treatments for this challenging disease, we will study pembrolizumab for the treatment of MRD in adults with ALL. This trial will offer an option to reduce the risk of frank relapse following either front-line or salvage therapy. Should this approach prove efficacious, it could create a novel method of treatment, in addition to providing a platform from which this agent could be tested either as a single-agent or in combination with other treatments as consolidation for patients in complete remission or for those with frankly relapsed/refractory ALL.

#### 4.2.3.2 Biomarker Research

ALL is relatively unique in that frequent disease assessments are common, relatively safe and non-invasive, and involve direct evaluation of the leukemia microenvironment (i.e., bone marrow). This provides an attractive opportunity to explore changes in the cellular and immunologic composition of tumor microenvironment before and after treatment with pembrolizumab. For example, since it has been demonstrated previously that PD-1 and PD-L1 expression on tumor cells and the tumor microenvironment is associated with a higher likelihood of response to inhibition of the PD-1/PD-L1 axis, we will be able to specifically evaluate the tumor microenvironment over time via bone marrow specimens. By definition, samples from patients on this study will have very little leukemia present, such that these analyses will be primarily reflective of the tumor microenvironment and not the malignancy *per se*.

9458- Protocol Version Date 28 Feb 2019

Further, to evaluate the systemic immune response more broadly, we can study changes in circulating PBMC and serum cytokines and inflammatory markers that occur following exposure to pembrolizumab to draw correlations to disease response (or lack thereof). Using a flow cytometry platform available in the UW Hematopathology Laboratory, relative proportions of circulating T-cell subsets and other components of cellular immunity can be quantified and compared pre- and post-treatment with pembrolizumab. Additionally, the Immune Monitoring Laboratory (IML) at the Fred Hutchinson Cancer Research Center (FHCRC) can measure the levels of approximately 40 different cytokines from samples of peripheral blood. Such analyses may provide evidence of an on-target *in vivo* effect in responding patients. They can also advance our understanding of why some patients respond to these agents while others seemingly do not, a phenomenon which has been suggested previously.

Lastly, while MFC and PCR remain the most widely-utilized methods of MRD detection in ALL, more sensitive methods are being developed. NGS platforms have been developed that can amplify and identify disease-specific index sequence from either the immunoglobulin heavy chain (IGH) or T-cell receptor (TCR) genes that are unique to individual B-cell and T-cell ALL (respectively). This technique can detect MRD with a frequency below  $10^{-5}$ , which is generally  $\geq 2$  orders of magnitude more sensitive than most clinically-available assays currently. Early studies suggest that detection even to this low level can impact outcomes in ALL. As this clinical trial is designed specifically for patients with MRD, it will provide a unique opportunity to further evaluate NGS as a viable method of MRD detection in ALL.

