### 5.1.3 Subject Exclusion Criteria

The subject must be excluded from participating in the trial if the subject:

1. Is currently participating and receiving study therapy or has participated in a study of an investigational new drug and received study therapy or used an investigational device within 4 weeks of the first dose of treatment.
2. Has a diagnosis of immunodeficiency or is receiving systemic steroid therapy or any other form of immunosuppressive therapy within 7 days prior to the first dose of trial treatment.
3. Has a known history of active TB (Bacillus Tuberculosis).
4. Has a known hypersensitivity to pembrolizumab or any of its excipients.
5. Has had a prior anti-cancer monoclonal antibody (mAb) within 4 weeks prior to study Day 1 or who has not recovered (i.e.,  $\leq$  Grade 1 or at baseline) from adverse events due to agents administered more than 4 weeks earlier.
6. Has had prior chemotherapy, targeted small molecule therapy, or radiation therapy within 2 weeks prior to study Day 1 or who has not recovered (i.e.,  $\leq$  Grade 1 or at baseline) from adverse events due to a previously administered agent.
  - Note: Subjects with  $\leq$  Grade 2 neuropathy or with hematologic toxicity that has recovered to levels above that stated in Inclusion Criterion 6 are an exception to this criterion and may qualify for the study if all other inclusion/exclusion criteria are met.
  - Note: If subject received major surgery, they must have recovered adequately from the toxicity and/or complications from the intervention (i.e.,  $\leq$  Grade 1 or at baseline) prior to starting therapy.
7. Has a known additional malignancy that is progressing or requires active treatment. Exceptions include basal cell carcinoma of the skin or squamous cell carcinoma of the skin that has undergone potentially curative therapy or in situ cervical cancer.
8. Has known active central nervous system (CNS) leukemia and/or leukemic meningitis. Subjects with previously treated CNS leukemia may participate provided they are stable (e.g., without evidence of active disease by imaging for at least four weeks prior to the first

9458- Protocol Version Date 28 Feb 2019

dose of trial treatment and any neurologic symptoms have returned to baseline) and have no evidence of leukemic blasts on analysis of cerebrospinal fluid (CSF).

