## 6.0 TRIAL FLOW CHART

### 6.1 Study Flow Chart

Trial Period:	Screening Phase	Treatment Cycles a								End of Treatment	Post-Treatment	
		1	2	3	4	To be repeated beyond 8 cycles					Discontinuation	Survival Follow-Up
Treatment Cycle/Title:	Screening Visit(s)					5	6	7	8			
Scheduling Window (Days):	-28 to -1		± 3	± 3	± 3	± 3	± 3	± 3	± 3	± 3	≤ 7 days post discontinuation	Every ~ 3 months
Administrative Procedures												
Informed Consent	X											
Inclusion/Exclusion Criteria	X											
Demographics and Medical History	X											
Prior and Concomitant Medication Review	X	X	X	X	X	X	X	X	X	X	X	
Pembrolizumab Administration		X	X	X	X	X	X	X	X	X		
Post-study anticancer therapy status												X
Survival Status												X
Clinical Procedures/Assessments												
Review Adverse Events	X	X d	X	X	X	X	X	X	X	X	X	
Full Physical Examination	X										X	
Directed Physical Examination		X d	X	X	X	X	X	X	X	X		
Vital Signs and Weight	X	X d	X	X	X	X	X	X	X	X	X	
ECOG Performance Status	X	X d	X	X	X	X	X	X	X	X	X	
Laboratory Procedures/Assessments: analysis performed by LOCAL laboratory												
Pregnancy Test – Urine or Serum β-HCG	X b											
PT/INR and aPTT	X b											
CBC with Differential	X b	X d	X	X	X	X	X	X	X	X	X	

9458- Protocol Version Date 28 Feb 2019

Trial Period:	Screening Phase	Treatment Cycles a								End of Treatment	Post-Treatment	
Treatment Cycle/Title:	Screening Visit(s)	1	2	3	4	To be repeated beyond 8 cycles				Discontinuation		Survival Follow-Up
						5	6	7	8			
Scheduling Window (Days):	-28 to -1		± 3	± 3	± 3	± 3	± 3	± 3	± 3	≤ 7 days post discontinuation		Every ~ 3 months
Comprehensive Serum Chemistry Panel	X b	X d	X	X	X	X	X	X	X	X		
Urinalysis	X b									X		
T3, FT4 and TSH	X b									X		
Efficacy Measurements												
Bone Marrow Examination	X	X e	X e		X e			X e,f		X e,f	X e	
Tumor Imaging	X c									X c		
Tumor Biopsies/Archival Tissue Collection/Correlative Studies Blood												
Archival or Newly Obtained Tissue Collection	X g	X g	X g		X g					X g		
Correlative Studies Blood Collection	X g		X g		X g					X g		

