### **7.1.2.7 Tissue Collection and Correlative Studies Blood Sampling**

Subjects who enroll on this study will have the option to provide tissue and blood samples for correlative studies, as described above in Section 4.2.3.2. Subjects may enroll on this study and opt out of these additional tests.

Bone marrow samples available from screening, post-cycle 1, post-cycle 2, post-cycle 4, and end-of-treatment will undergo DNA extraction in order to perform NGS-based MRD assessments. As these assays require knowledge of the leukemia-specific sequence from a sample with relatively high disease burden (e.g., initial diagnosis or morphologic relapse), archived tissue will be requested in order to identify this. In the event that this baseline sample cannot be obtained, then collection of samples for these exploratory MRD assessments may be deferred at the discretion of the PI. Lastly, DNA will be extracted from bone marrow obtained post-cycle 4 (for those patients still enrolled at that time) to investigate for clonal changes in the immune microenvironment.

As close as feasible to the timing of these marrow examinations at screening, post-cycle 2, post-cycle 4, and end-of-treatment, peripheral blood will also be collected for additional correlative studies. Flow cytometry will be performed in the UW Hematopathology Laboratory to assess for changes in circulating T-cell subsets (e.g., cytotoxic T cells, regulatory T cells) and other markers of cellular immunologic response. DNA will also be extracted to investigate for clonal changes in the immune repertoire. Lastly, cytokine and inflammatory marker measurements will occur in the IML at FHCRC and can include (but not necessarily limited to) PD-L1, interleukin (IL)-2, IL-21, and tumor necrosis factor alpha.

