### **7.1.3 Laboratory Procedures/Assessments**

Details regarding specific laboratory procedures/assessments to be performed in this trial are provided below.

Laboratory tests for hematology, chemistry, urinalysis, and others are specified in Table 5.

9458- Protocol Version Date 28 Feb 2019

Table 5: Laboratory Tests

Hematology	Chemistry	Urinalysis	Other
Hematocrit	Albumin	Blood	Serum $\beta$ -human chorionic gonadotropin†
Hemoglobin	Alkaline phosphatase	Glucose	( $\beta$ -hCG)†
Platelet count	Alanine aminotransferase (ALT)	Protein	PT (INR)
WBC (total and differential)	Aspartate aminotransferase (AST)	Specific gravity	aPTT
Red Blood Cell Count	Lactate dehydrogenase (LDH)	Microscopic exam ( If abnormal, results are noted )	Total triiodothyronine (T3)
Absolute Neutrophil Count	Carbon Dioxide	Urine pregnancy test †	Free thyroxine (T4)
Absolute Lymphocyte Count	( CO2 or biocarbonate )		Thyroid stimulating hormone (TSH)
	Uric Acid		
	Calcium		
	Chloride		Blood for correlative studies
	Glucose		
	Phosphorus		
	Potassium		
	Sodium		
	Magnesium		
	Total Bilirubin		
	Direct Bilirubin ( If total bilirubin is elevated above the upper limit of normal )		
	Total protein		
	Blood Urea Nitrogen		

† Perform on women of childbearing potential only. If urine pregnancy results cannot be confirmed as negative, a serum pregnancy test will be required.

9458- Protocol Version Date 28 Feb 2019

Laboratory tests for screening or entry into the Second Course Phase should be performed within 10 days prior to the first dose of treatment. After Cycle 1, pre-dose laboratory procedures can be conducted up to 3 days prior to dosing. Results must be reviewed by the investigator or qualified designee and found to be acceptable prior to each dose of trial treatment.

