##### **7.1.5.1 Screening**

###### **7.1.5.1.1 Screening Period**

Screening evaluations as listed in Section 6.0 - Trial Flow Chart may occur within 28 days of initiation of treatment, with the following two exceptions: laboratory assessments (as mentioned above) should be obtained within 10 days, and urine/serum pregnancy test must be performed within 3 days of the first dose of pembrolizumab.

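### Exploratory immune baseline: the only pre-treatment blood is tied to the screening marrow (up to 28 or 10 days before dose 1, depending on the section), so off-drug recovery can enter the pre/post change

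*Combined protocol and SAP*

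**What the plan says.** **Purpose.** Exploratory objective 2 (Section 3.3) expects changes in blood mononuclear cells and cytokines to predict immune response and anti-leukemia efficacy. Section 4.2.3.2 adds that "relative proportions of circulating T-cell subsets and other components of cellular immunity can be quantified and compared pre- and post-treatment with pembrolizumab".

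**Sampling.** Section 7.1.2.7 times the blood "As close as feasible to the timing of these marrow examinations at screening, post-cycle 2, post-cycle 4, and end-of-treatment". The flow-chart row "Correlative Studies Blood Collection" is marked at Screening, Cycle 2, Cycle 4 and end of treatment, and is blank at Cycle 1. It carries footnote g only, not footnote b, which sets the 10-day limit.

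**Age of the baseline sample.** The flow chart gives a screening window of Day -28 to -1, and Section 7.1.2.6 accepts a marrow up to 28 days old. Section 7.1.5.1.1 says screening evaluations "may occur within 28 days of initiation of treatment", but then limits laboratory assessments to 10 days. Table 5 (Section 7.1.3) includes the correlative blood among the laboratory tests, and the text below it repeats the 10-day limit for screening laboratory tests.

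**Washouts.** In Section 5.1.3, criterion 6 reads "Has had prior chemotherapy, targeted small molecule therapy, or radiation therapy within 2 weeks prior to study Day 1", and criterion 2 covers a patient who "is receiving systemic steroid therapy or any other form of immunosuppressive therapy within 7 days prior to the first dose of trial treatment". Section 5.5.2 bars chemotherapy and, with exceptions, systemic glucocorticoids during the Screening Phase, and refers to the exclusion criteria for other prohibited drugs.

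**Analysis.** The trial has a single arm (Section 1.0). Section 9.2 says biomarker reporting will be mainly descriptive and plans no adjustment for time since prior therapy.

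**The concern.** In a single arm, a before/after difference can be credited to the drug only if little else changes between the two samples. Here the baseline may be taken well before dose 1, and nothing fixes how long the patient must have been off prior treatment when it is drawn. Section 5.1.2 admits patients with persistent MRD as early as 2 weeks after the start of salvage therapy, so recent treatment is an intended route into the trial. In such patients T-cell subsets and cytokines may shift between screening and dose 1 with no study drug on board.

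Two readings are at stake. The average change could be taken for an on-target immune effect. And because recovery depends on time since prior therapy, which differs between patients and may itself be related to outcome, it could produce or hide a correlation with MRD response. A pre-dose sample that was never drawn cannot be obtained later.

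**Working it through.** The plan gives no sample size, effect size or test for this comparison, so there is no figure of its own to reproduce. The check is calendar arithmetic.

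**Inputs.** Cycle length 21 days (Section 5.2). Post-cycle sample on Day 18-20 of the cycle (Section 7.1.2.6). Largest gap from baseline to dose 1: 28 or 10 days, as set out above. Washouts: 14 days (chemotherapy) and 7 days (steroids, immunosuppression).

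**Share of the interval before any drug.** Cycle 2 starts 21 days after dose 1, and Day 18-20 falls 17-19 days into the cycle. The post-cycle 2 sample is therefore 21 + 17 = 38 to 21 + 19 = 40 days after dose 1. Share = gap / (gap + 38 to 40).

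| Baseline | Gap | Interval to post-cycle 2 | Share before drug |
|---|---|---|---|
| 28-day reading | 28 days | 66-68 days | 28/68 to 28/66 = 41-42% |
| 10-day reading | 10 days | 48-50 days | 10/50 to 10/48 = 20-21% |
| Cycle 1 Day 1, pre-dose | 0 | 38-40 days | 0% |

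These are maxima; under either reading the sample may be as late as Day -1.

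**Shortest time from last prior therapy to baseline** = washout minus gap, on Section 5.1.3 alone. A negative value means that the sample precedes the last dose.

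| Prior therapy | 28-day reading | 10-day reading | Cycle 1 Day 1 |
|---|---|---|---|
| Chemotherapy | 14 - 28 = -14 days | 14 - 10 = 4 days | 14 days |
| Steroids, immunosuppression | 7 - 28 = -21 days | 7 - 10 = -3 days | 7 days |

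If the Section 5.5.2 ban is applied, chemotherapy and steroids have stopped by screening, but on the 28-day reading the sample could still follow directly on the last dose. These passages need to be reconciled.

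**Sensitivity to drift (assumed; the documents give no recovery rate and plan no such test).** Suppose there is no drug effect, but the pre-dose drift equals a given fraction of the SD of the paired change. A two-sided 5% paired t-test would then report a change this often:

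| Assumed drift (SD) | 12 pairs | 21 pairs |
|---|---|---|
| 0 | 5% | 5% |
| 0.25 | 12% | 19% |
| 0.5 | 35% | 59% |
| 1.0 | 88% | 99% |

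**Proportions (assumed counts).** If CD8 cells stay at 200/uL while other lymphocytes rise from 300 to 700/uL, the CD8 share falls from 200/500 = 40% to 200/900 = 22% with no change in CD8 number.

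**The case against.** The case for leaving the plan alone has weight, and several parts of it stand.

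- A reader might infer that the baseline is simply a 28-day-old sample that may be drawn right at the end of chemotherapy. The documents do not settle that. Table 5 and its text support 10 days, which halves the pre-drug share and puts the sample at least 4 days after chemotherapy. What stands is an unresolved conflict, and neither reading brings the gap to zero.
- A reader might infer that non-steroid immunosuppressants are unrestricted during screening because the Section 5.5.2 bullets omit them. That section sends the reader to the exclusion criteria, and criterion 2 names them. Its limit is 7 days before dose 1, so how far it reaches across screening is arguable.
- A reader might infer that relative proportions are the planned measure. That wording is rationale text. Section 7.1.2.7 speaks only of changes in subsets, and Table 5 already includes "Absolute Lymphocyte Count". Cytokine levels are not proportions at all.
- A reader might infer that every change will be read as a drug effect. The plan makes no such claim; it calls the evidence possible and the reporting descriptive.
- Drawing blood close to the marrow is a defensible preference. The loss at baseline is small, because Section 7.1.2.7 uses the screening marrow for sequencing-based MRD.
- The samples are optional, at most 21 patients are planned, and no primary, safety or stopping decision uses them. This limits the weight of the point.

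**Conclusion.** The point holds as a limited design weakness. The only baseline research blood is tied to the screening marrow, no pre-dose sample is scheduled on Cycle 1 Day 1, and the washouts protect dose 1 but not the sample. Up to 41-42% of the baseline to post-cycle 2 interval, or 20-21% under the 10-day reading, can pass before any drug. In patients recently off therapy, recovery in that time cannot be told apart from a drug effect with one arm and no planned adjustment.

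It would go too far to conclude that the pre/post comparisons are biased across the trial. Section 5.1.2 also admits MRD reappearance at any time, so some patients may be long off treatment. The documents give no recovery rate, so the size of the bias is unknown, and a false correlation with response is a possibility only. The drift table and the CD8 example rest on assumed values. The shares assume nominal 21-day cycles. The consequence is confined to exploratory objective 2.

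**What to change.** 1. In Section 7.1.2.7 and the flow chart, move the baseline correlative blood to Cycle 1 Day 1 before infusion and define it as the pre-treatment value. Give the new Cycle 1 entry its own footnote saying that it is pre-dose, because the marrow entry in that column refers to the end of the cycle. This also removes the 10-day versus 28-day conflict for this sample.
2. Take a CBC with differential at the same draw, even when footnote d waives the other Cycle 1 laboratory tests.
3. Add one sentence of analysis text: report absolute subset counts (flow proportion of lymphocytes x absolute lymphocyte count) beside the proportions, and describe changes by time since prior therapy, using the treatment history already recorded under Sections 7.1.1.4 and 7.1.1.5.
4. For samples already collected, apply item 3 alone, with the lymphocyte count closest in time.

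**Cost.** The number of research tubes is unchanged and the infusion visit already exists; at most one CBC is added where footnote d would have waived it. Baseline blood would no longer be concurrent with the screening marrow.

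**What remains.** Only the pre-dose part of the drift is removed. A Day 1 sample may still come 14 days after chemotherapy or, under exclusion criterion 2, 7 days after steroids or immunosuppression. Recovery that continues after dose 1 stays mixed with drug effect, and any report of these data should say so.
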